11.4.1.2 Response at 6 months – Sensitivity analyses

- a) The analysis presented in §11.4.1.1 will be performed on PP population
- b) The analysis presented in §11.4.1.1 will be performed on the response at 6 months computed by Soladis.
- c) The analysis presented in §11.4.1.1 will be performed on the response at 6 months based on the PI response, but excluding patients 06-07, 06-08 and 06-09.
- d) The analysis presented in §11.4.1.1 will be performed on the response at 6 months computed by Soladis, but excluding patients 06-07, 06-08 and 06-09.

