### **10.2. Analyses data set**

Every patient included in the study and who has received at least one infusion of ATO will be taken into account at time of data analysis.

Patients who do not receive any injection of ATO will not be analyzed and will be replaced to obtain 24 patients provided in the statistical analysis.

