### **10.7. Calculation of the number of patients**

Based on results from the literature, the hypothesis for the primary endpoint is an improvement in response rate (CR and PR) at 6 months after the diagnosis of chronic GvHD and start of ATO from 60% to 85%. Using a one-step A'Hern procedure (A'Hern RP, 2001) (and anticipating a dropout rate around 10%), 24 (21+3) patients are needed. If the number of successful cases is 17 or more among the 21 patients, the hypothesis that the CR rate at 6 months is less than 60% is rejected with a target error rate of 0.05 (alpha probability). The beta probability in this case is 0.2.

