12.4.3.5 Determination of sample size

The aim of this study is to assess whether ATO allows improving response rate at 6 months after the diagnosis of chronic GVHD from 60% to 85%.

For the sample size calculation in this trial, an A'Hern one stage design has been used (ref 1).

- Let P_0 be the smallest response rate, if true, implies that the role of ATO is too low and therefore the present schedule does not warrant further investigation. In the present trial, P_0 has been taken as 60%.
- Let P_1 be the highest response rate which, if true, implies that the feasibility is sufficiently high and therefore the current schedule warrants further investigation in clinical trials. In the present trial, P_1 has been taken as 85%;
- Let α be the accepted probability of recommending for further investigation a regimen with a true discontinuation rate at least equal to P_0 . In the present trial, α has been taken as 0.05.
- Let β be the accepted probability of rejecting for further investigation a regimen with a true discontinuation rate less than P_1 . In the present trial, β has been taken as 0.20.

The required number of eligible patients is 21. To compensate for a dropout of 10%, 24 patients are planned to be included.

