11. EFFICACY EVALUATION

11.1 ANALYSES POPULATIONS

Every patient included in the study and who has received at least one infusion of ATO will be taken into account at time of data analysis.

The number of patients included who did not receive any infusion of ATO will be reported as well as the reason for not receiving ATO.

The following analyses populations will be considered:

- The safety population consists of all patients included in the study for whom there is any evidence that they used at least one ATO injection.
- The Full Analysis Set (FAS) population consists of included subjects who completed their first cycle of ATO and for whom the response at Week 6 after diagnosis of chronic GvHD has been evaluated.
- The Per Protocol (PP) population will exclude FAS patients with any major protocol deviations that may impact the efficacy analysis. The exclusion of patients from the PP population will be determined during the final data review meeting. Reason(s) for exclusion will be documented for each patient.

The following table will be presented:

Analysis set (N=XX)	
Safety Population	n/N (XX.XX%)
Full Set Analysis Population	n/N (XX.XX%)
Per Protocol Population	n/N (XX.XX%)

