14.2.2 Sensitivity analyses		
14.2.2.1	PP	Complete or partial response at 6 months (PI response) – Overall
14.2.2.2	PP	Complete and partial response at 6 months (PI response) – Overall
14.2.2.3	FAS	Complete or partial response at 6 months (computed response) – Overall
14.2.2.4	FAS	Complete and partial response at 6 months (computed response) – Overall
14.2.2.5	FAS	Complete or partial response at 6 months (computed response) – By sex
14.2.2.6	FAS	Complete and partial response at 6 months (computed response) – By sex
14.2.2.7	FAS	Complete or partial response at 6 months (computed response) – By center
14.2.2.8	FAS	Complete and partial response at 6 months (computed response) – By center
14.2.2.9	FAS	Complete or partial response at 6 months (computed response) – By number of cycles of ATO
14.2.2.10	FAS	Complete and partial response at 6 months (computed response) – By number of cycles of ATO
14.2.2.11	FAS	Complete or partial response at 6 months (computed response) – By use of Ciclosporin or not
14.2.2.12	FAS	Complete and partial response at 6 months (computed response) – By use of Ciclosporin or not
14.2.2.13	FAS	Complete or partial response at 6 months (computed response) – By number of organs involved in cGvHD
14.2.2.14	FAS	Complete and partial response at 6 months (computed response) – By number of organs involved in cGvHD
14.2.2.15	FAS	Complete or partial response at 6 months (computed response) – By GvHD severity at baseline
14.2.2.16	FAS	Complete and partial response at 6 months (computed response) – By GvHD severity at baseline
14.2.2.17	FAS	Complete or partial response at 6 months (PI response) without patients 06-07, 06-08 and 06-09 – Overall
14.2.2.18	FAS	Complete and partial response at 6 months (PI response) without patients 06-07, 06-08 and 06-09 – Overall
14.2.2.19	FAS	Complete or partial response at 6 months (computed response) without patients 06-07, 06-08 and 06-09 – Overall

Table Number	Population	Table Title / Summary
14.2.2.20	FAS	Complete and partial response at 6 months (computed response) without patients 06-07, 06-08 and 06-09 – Overall

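### Two sensitivity analyses repeat the primary test without three patients named by number, with no stated criterion and outside the per-protocol route

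*SAP*

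**What the plan says.** SAP 11.4.1.2 lists four sensitivity analyses of response at 6 months. Analysis a) uses the per-protocol (PP) set and b) uses the computed response. Analysis c) is "based on the PI response, but excluding patients 06-07, 06-08 and 06-09" and d) is "computed by Soladis, but excluding patients 06-07, 06-08 and 06-09". Each repeats section 11.4.1.1, which contains the test of the 60% null by a 95% Clopper-Pearson interval. The table list (14.2.2.17 to 14.2.2.20) repeats the exclusion, "without patients 06-07, 06-08 and 06-09", under the population label FAS. Figures 14.2.2.3 and 14.2.2.4 do the same.

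No section supplied gives a criterion, a deviation or a reason for removing these three. SAP 11.1 already has a route for leaving patients out. The PP set drops those with major deviations, as decided at the final data review meeting, and "Reason(s) for exclusion will be documented for each patient".

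Protocol 10.2 sets the general principle: "Every patient included in the study and who has received at least one infusion of ATO will be taken into account". The success rule in Protocol 10.7 begins "If the number of successful cases is 17 or more among the 21 patients". The documents give no cut-off for 24 or any other number.

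**The concern.** A sensitivity analysis is useful when the reader knows which assumption it varies. Here the reader knows only which patients leave. If the three had a major deviation, analysis a) already removes them. If they did not, the SAP gives no basis for removing them.

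The trial has no blinding, and the main response is the investigator's judgement. In that setting a patient-level exclusion needs a criterion that does not depend on response. Without one, a justified data-quality check cannot be told apart from the removal of poor outcomes.

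The numbers sharpen the point. Twenty-four patients are planned, and 24 − 3 = 21 is the one denominator for which the protocol states a success rule. The shared prefix 06 suggests a single site, but the documents do not define the numbering.

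**Working it through.** **Inputs.** The design concerns "improving response rate at 6 months after the diagnosis of chronic GVHD from 60% to 85"% (SAP 12.4.3.5), so p0 = 0.60 and p1 = 0.85. The rule is 17 of 21, and the null "is rejected with a target error rate of 0.05 (alpha probability") (Protocol 10.7). Planned N is 24. Three patients are removed. Two assumptions are mine: that all 24 are in the FAS, whose size is not given, and that the number of responders among the three, k, may be anything from 0 to 3.

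**Formulas.** One-sided exact p = Σ C(n,x)·0.6^x·0.4^(n−x), summed from the observed count to n. The 95% Clopper-Pearson lower bound is the 2.5% quantile of Beta(x, n−x+1).

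**The plan's own figure.** For 17 of 21: 0.02593 + 0.00865 + 0.00205 + 0.00031 + 0.00002 = 0.0370, within 0.05. Power at 85% is 0.8025. With dropout, 21/0.90 = 23.3, so 24. The design reproduces.

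**Two yardsticks.** The protocol rule is 17 of 21. With 24 patients, the exact cut-off at a one-sided 0.05 is 19 (attained alpha 0.040); I computed this because the documents state none. The SAP rule compares the lower bound with 60%. SAP 11.4.1.1 prints the direction reversed, rejecting when the bound is below 60%; I read it as above 60%. That requires 18/21 (63.7%) or 20/24 (62.6%).

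**Effect of removing the three.**

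| All 24: p, lower bound | k | Remaining 21: p, lower bound | Protocol rule | SAP rule |
|---|---|---|---|---|
| 17/24: 0.192, 48.9% | 0 | 17/21: 0.037, 58.1% | fail → pass | fail → fail |
| 17/24 | 1 | 16/21: 0.096, 52.8% | fail → fail | fail → fail |
| 18/24: 0.096, 53.3% | 0 | 18/21: 0.011, 63.7% | fail → pass | fail → pass |
| 18/24 | 1 | 17/21: 0.037, 58.1% | fail → pass | fail → fail |
| 18/24 | 2 | 16/21: 0.096, 52.8% | fail → fail | fail → fail |
| 18/24 | 3 | 15/21: 0.200, 47.8% | fail → fail | fail → fail |
| 19/24: 0.040, 57.8% | 0 | 19/21: 0.002, 69.6% | pass → pass | fail → pass |
| 19/24 | 1 | 18/21: 0.011, 63.7% | pass → pass | fail → pass |
| 19/24 | 2 | 17/21: 0.037, 58.1% | pass → pass | fail → fail |
| 19/24 | 3 | 16/21: 0.096, 52.8% | pass → fail | fail → fail |

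With k of 0 or 1, removal can turn a failure into a success. With k of 2 or 3 it cannot, if the same rule is used before and after, and with k = 3 it can turn a success into a failure.

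**The case against.** The strongest reply is that nothing decisive depends on c) and d). The main analysis in SAP 11.4.1.1 keeps the three patients, and c) and d) are labelled as sensitivity analyses. An additional analysis does not breach Protocol 10.2. The direction of any effect is unknown, so removal might be the conservative check. Three consecutive numbers fit an enrolment or site reason as well as any other. Listings of deviations, eligibility and populations are planned. All of this stands, and it limits the point to the interpretability of two supportive analyses.

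Four stronger readings are tempting and are not supported.

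- **That the exclusion rescues a failed trial at 17 of 21.** 17/21 meets the protocol rule, but its lower bound of 58.1% fails the SAP rule in its sensible direction. The primary result does not change in any case.
- **That the type I error rises to 19%.** P(X ≥ 17 of 24 at 60%) = 0.192 is the chance of reaching 17 of 21 only if the three were picked because they failed. For three patients fixed independently of outcome, it is 0.037.
- **That the text was written with these patients' responses in view.** Numbers on the page show that the individuals had been identified. The response algorithm in SAP 17.1 is dated 19 October 2020, after the planned last visit of June 2020. However, Protocol 10.1 requires the SAP to be signed before database lock, and nothing says the month-6 responses were known.
- **That the three should also be analysed as failures.** This would recode any observed responder, and it tests no plausible scenario.

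The reply does not supply the reason itself. It could be given in one sentence, and until it is, the hypothesis decision in c) and d) cannot be interpreted.

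**Conclusion.** The point holds as a defect in two supportive analyses, not in the primary one. SAP 11.4.1.2 c) and d) rerun a hypothesis decision on a set chosen by patient number, with no criterion and outside the route that requires one.

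If 24 patients are in the FAS and all three are non-responders, 18/24 becomes 18/21 and crosses both thresholds, while 17/24 becomes 17/21 and meets only the protocol's. These figures rest on the assumed FAS size, on outcomes that the documents do not give, on a cut-off for 24 that I computed, and on the SAP rule read in its sensible direction. That no reason is stated in the supplied text rests on none of these.

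**What to change.** Amend SAP 11.4.1.2 before database lock:

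1. State the criterion that the three patients meet, in terms that do not depend on response. Say when it was decided and whether their month-6 responses were known then.
2. Apply that criterion to all patients at all sites through the PP set, with reasons recorded as SAP 11.1 requires.
3. If there is no such criterion, delete c) and d), or label them post hoc and descriptive.
4. In every case, add that no rejection of the null and no claim of success may rest on c) or d).
5. If the outputs are kept, stop labelling Tables 14.2.2.17 to 14.2.2.20 and Figures 14.2.2.3 and 14.2.2.4 simply as FAS.

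The cost is SAP wording, with no new data. The sponsor may lose a supportive presentation that could have been favourable.

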11.4.2 Secondary Endpoint analyses

11.4.2.1 Response by organ

The proportion of response at 6 months (Complete, partial or progressive) will be estimated and presented for each organ. No response is evaluated for an organ when no abnormalities is present at V1, except progressive disease.

Derivation

Derived variables	Definition
Complete response for each organ	Cf Appendix 1 “Evaluation de la réponse – 19OCT2020”
Partial response for each organ	
Progressive disease	
Organ not involved at any moment	

The following table will be presented:

Organ	Response at M6	FAS Population (N = XX)
Organ 1	Complete response	n/N (XX.X%)
	Partial response	n/N (XX.X%)
	Progressive disease	n/N (XX.X%)
	Organ not involved at any moment	n/N (XX.X%)

This table will be completed for skin, mouth, lung, eyes, gastro-intestinal, liver and joint & fascia.

11.4.2.2 Survival analyses

a) Failure free survival

A survival analysis will be conducted to describe the occurrence of failure between the first infusion of ATO and Vi, with Vi={M6;M12}.

Derivation

Derived variables	Definition
Failure at Vi Calculated at Vi={M6;M12}	Defined as death, recurrent or progressive malignancy, or the initiation of a new systemic treatment for chronic GvHD. Systemic treatment are: Methotrexate, Rapamune, TLI, Extracorporeal photopheresis, Rituximab, Jakavi, Glivec, Prograf, Imurel or other medications specified into the CRF (Vi_RESP_FAIL and or Vi_RESP_FAIL_S)
Time calculation from first ATO infusion to failure at Vi Calculated at Vi={M6;M12}	If the event appears: the difference of date between the first ATO infusion and the first failure (expressed in months) is calculated. The event will be not censored. $(\text{Date of first ATO infusion} - \text{Date of first failure})/30.5$ If the event does not appear, the difference of date between the first ATO infusion and Vi (expressed in months) is calculated. The event will be censored.

The following table will be presented at M6:

FAS Population

(N = XX)

First time of failure between first ATO infusion and M6 (in months)	n/M (%) of events	n/N (XX.XX%)
	n/M (%) of censored	n/N (XX.XX%)

The Kaplan-Meier survival estimates will be plotted with the number of subjects at risk and 95% confidence limits.

These analyses will be also presented at M12.

b) Progression free survival

A survival analysis will be conducted to describe the occurrence of progression between the first infusion of ATO and Vi, with Vi={M6;M12}.

Derivation

Derived variables	Definition
Progressive disease at Vi Calculated at Vi={M6;M12}	Global progressive disease as define in Appendix 17.1
Time calculation from first ATO infusion to failure at Vi Calculated at Vi={M6;M12}	If the event appears: the difference of date between the first ATO infusion and the first progression (expressed in months) is calculated. The event will be not censored. $(\text{Date of first ATO infusion} - \text{Date of first progression})/30.5$ If the event does not appear, the difference of date between the first ATO infusion and Vi (expressed in months) is calculated. The event will be censored.

The following table will be presented at M6:

FAS Population		
(N = XX)		
First time of progression between first ATO infusion and M6 (in months)	n/M (%) of events	n/N (XX.XX%)
	n/M (%) of censored	n/N (XX.XX%)

The Kaplan-Meier survival estimates will be plotted with the number of subjects at risk and 95% confidence limits.

These analyses will be also presented at M12.

c) Overall survival

A survival analysis will be conducted to describe the occurrence of death between the first infusion of ATO and Vi, with Vi={M6;M12}.

Derivation

Derived variables	Definition
Death at Vi Calculated at Vi={M6;M12}	Yes, if the death occurs between the first ATO infusion and Vi
Time calculation from first ATO infusion to death at Vi Calculated at Vi={M6;M12}	If the event appears: the difference of date between the first ATO infusion and the date of death (expressed in months) is calculated. The event will be not censored. (Date of first ATO infusion – Date of death)/30.5 If the event does not appear, the difference of date between the first ATO infusion and Vi (expressed in months) is calculated. The event will be censored.

The following table will be presented at M6:

FAS Population		
(N = XX)		
Death between first ATO infusion and M6 (in months)	n/M (%) of events	n/N (XX.XX%)
	n/M (%) of censored	n/N (XX.XX%)

The Kaplan-Meier survival estimates will be plotted with the number of subjects at risk and 95% confidence limits.

These analyses will be also presented at M12.

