#### **4.3 Withdrawal/premature discontinuation criteria**

A premature discontinuation is defined when a patient selected in a study ceases his/her participation before the end of study.

The criteria for premature discontinuation of the study are:

- Withdrawal of informed consent
- Lost to follow-up
- Occurrence of AE/SAE
- Inclusion criteria not met requiring premature discontinuation
- Protocol deviation
- Other reason

Patients who do not receive any injection of ATO will not be analyzed and will be replaced to obtain the total 24 patients required in the statistical analysis.

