### **10.5. Missing data handling**

Every effort will be made to keep the number of missing values for all parameters to a minimum. Missing data on overall survival is assumed to be 0 as patient care after transplantation is very close.

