12.4.3.2 Handling of Dropouts or Missing Data

Every effort will be made to keep the number of missing values for all parameters to a minimum. The number of missing values will be reported together with summary statistics for each variable.

Missing data on overall survival is assumed to be null as patient care after transplantation is very close. Any patient prematurely withdrawn or ending the study without the event of interest (progression, death) will be censored at his/her last information date.

Concerning the main endpoint (response at M6), the missing assessments will be fully discussed during the data review. The most plausible outcome (the clinically more relevant) will be used for the main analysis. Other methods of imputation (for example, worst

outcome: missing data=failure) could be used for sensitivity purpose, according to the final number of missing assessments.

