10. PATIENTS

10.1 DISPOSITION OF PATIENTS

All patients screened and receiving at least one infusion of ATO will be accounted for.

Derivation

Derived variables	Definition
Study completed	Yes, if the patient is present in the study at M12 No, if the patient is not present in the study at M12

The following table will be then presented:

	Analysis set (N=XX)
Study completed	n/N (XX.XX%)
Withdrawal of informed consent	n/N (XX.XX%)
Lost to follow-up	n/N (XX.XX%)
Occurrence of AE/SAE requiring premature discontinuation	n/N (XX.XX%)
Inclusion criteria not met requiring premature discontinuation	n/N (XX.XX%)
Other reason	n/N (XX.XX%)

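### SAP 11.4.2.2 censors event-free patients at M6 or M12 with no exception for early leavers, which conflicts with the last-information-date rule in SAP 12.4.3.2, and it prints event times with the sign reversed

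*SAP*

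**What the plan says.** SAP 11.4.2.2 derives time to event separately for failure-free survival (a), progression-free survival (b) and overall survival (c), each at M6 and at M12. The censoring sentence is the same in all three: "If the event does not appear, the difference of date between the first ATO infusion and Vi (expressed in months) is calculated", and the observation is then censored. None of the three mentions withdrawal, the last information date or SAP 12.4.3.2.

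SAP 12.4.3.2 has a different rule: "Any patient prematurely withdrawn or ending the study without the event of interest (progression, death) will be censored at his/her last information date".

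The event times in 11.4.2.2 are printed as first infusion minus event date. For overall survival the formula reads "Date of first ATO infusion – Date of death)/30.5", and the other two have the same order.

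Both documents foresee patients who leave early. SAP 12.4.3.5 says "To compensate for a dropout of 10%, 24 patients are planned to be included". SAP 10.1 codes study completion as "No, if the patient is not present in the study at M12". Protocol 4.3 lists "Lost to follow-up" and withdrawal of consent among the reasons for premature discontinuation. For overall survival only, Protocol 10.5 states "Missing data on overall survival is assumed to be 0 as patient care after transplantation is very close", and SAP 12.4.3.2 repeats the assumption.

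**The concern.** A patient who leaves event-free before Vi has no Vi visit, and the SAP does not say what date Vi then takes. A programmer working from the derivation table could use the nominal 6 or 12 months, which counts the patient as observed and event-free to that point. Or the time could be left missing, which removes the patient from the curve. Missing is the SAP's own convention for other date differences (11.3.1, 11.3.2) and for visits that match no prednisone record (11.4.2.3). Neither result is what 12.4.3.2 prescribes.

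This is a single-arm trial, so the absolute Kaplan-Meier estimates are the result for these secondary endpoints. Relative to last-information censoring, nominal-Vi censoring can only leave the estimate unchanged or raise it. The planned tables of event and censored counts would not show that this had happened.

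**Working it through.** **No stated figure to reproduce.** The documents give no rate, event count or power for these endpoints. The one related figure is the dropout allowance: 21/(1 − 0.10) = 23.3, rounded up to 24, which allows for 24 − 21 = 3 dropouts.

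**Inputs from the documents.** N = 24, m = 3 leavers, and 30.5 days per month. The survival tables use the FAS, which requires a completed first cycle and an evaluated Week 6 response (SAP 11.1). Leaving at month 2 (2 × 30.5 = 61 days) is later than Week 6 (42 days), so such a patient can be in the FAS.

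**Assumptions.** The number and timing of failures, the time of leaving, and all 24 patients being in the FAS.

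**Formulas for 12-month failure-free survival.** Let a be the failures before the leavers go, b the failures after, and d = a + b.
- Censored at last information: (N − a)/N × (N − a − m − b)/(N − a − m)
- Censored at nominal Vi, so that leavers stay at risk to the end: (N − d)/N
- Time missing, leavers removed: (N − m − d)/(N − m)

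Differences from last-information censoring, in percentage points from unrounded values, are in brackets.

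| Leave at | d (a, b) | Last information | Nominal Vi | Removed |
|---|---|---|---|---|
| Month 2 | 6 (0, 6) | 15/21 = 71.4% | 18/24 = 75.0% (+3.6) | 15/21 = 71.4% (0) |
| Month 2 | 8 (0, 8) | 13/21 = 61.9% | 16/24 = 66.7% (+4.8) | 13/21 = 61.9% (0) |
| Month 2 | 10 (0, 10) | 11/21 = 52.4% | 14/24 = 58.3% (+6.0) | 11/21 = 52.4% (0) |
| Month 9 | 6 (4, 2) | 20/24 × 15/17 = 73.5% | 18/24 = 75.0% (+1.5) | 15/21 = 71.4% (−2.1) |
| Month 9 | 8 (6, 2) | 18/24 × 13/15 = 65.0% | 16/24 = 66.7% (+1.7) | 13/21 = 61.9% (−3.1) |
| Month 9 | 10 (8, 2) | 16/24 × 11/13 = 56.4% | 14/24 = 58.3% (+1.9) | 11/21 = 52.4% (−4.0) |

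**Sensitivity of the nominal-Vi shift.**
- One of 6 failures before a month-2 departure: 23/24 × 15/20 = 71.9%, so +3.1.
- Month-2 leavers with 4 failures: 20/24 − 17/21 = +2.4. With 12 failures: 12/24 − 9/21 = +7.1.
- Month-9 leavers with 4 failures (3, 1): 20/24 − 21/24 × 17/18 = +0.7. With 12 failures (9, 3): 12/24 − 15/24 × 9/12 = +3.1.
- A smaller FAS of 21 with 2 early leavers and 8 later failures: 13/21 − 11/19 = 61.9% − 57.9% = +4.0.
- m = 0: all three formulas give the same value, and the shift is zero.

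**Sign of the event time.** For a failure at month 4 (4 × 30.5 = 122 days after first infusion), the printed formula gives −122/30.5 = −4.0 months. Event date minus first infusion gives +4.0.

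**The case against.** The strongest defence is that the two sections complement each other: 12.4.3.2 governs early leavers, and 11.4.2.2 covers patients followed to the landmark, for whom censoring at Vi is correct. A reader might infer that the SAP leaves a programmer only two wrong options. That is too strong, because the right rule is written in 12.4.3.2. But 11.4.2.2 is worded for every patient without an event, neither section says which prevails, and the derivation table is what would be programmed. Even if 12.4.3.2 governs, the derivations need correcting to match it.

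A reader might also infer a bias of about 10 points. Reaching that takes 5 leavers out of 24, about double the planned 10%: with 10 failures, two of them by month 2, 22/24 × 9/17 = 48.5% against 14/24 = 58.3%. The planned rate does not support it.

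Nor do the documents support the inference that all three endpoints would be inflated against historical benchmarks. Their historical rate of 60% is for response, and they state none for failure-free, progression-free or overall survival. Overall survival data are assumed complete, and the dropout allowance belongs to the response sample size, so it is not evidence of lost vital status. The FAS already excludes patients who leave before Week 6.

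The reversed subtraction is a separate notation error. The adjacent prose makes the intended interval plain, and a programmer would probably notice. It adds no weight to the censoring point, but it sits in the same cells and needs the same edit.

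**Conclusion.** Wrong as written. The censoring sentence in 11.4.2.2 gives event-free leavers a time that conflicts with SAP 12.4.3.2, and the printed event-time formulas give negative durations.

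The practical size is modest. With 24 patients, 3 leavers and 6 to 10 failures, nominal-Vi censoring adds about 3 to 6 points to 12-month failure-free survival for departures at month 2 and about 1 to 2 points for departures at month 9. Allowing 4 to 12 failures, the shift runs from +0.7 to +7.1 points. Removing leavers changes the estimate by between 0 and about −4 points. All of this rests on assumed events and departure times.

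The endpoints affected are secondary and descriptive. The primary response analysis does not use these derivations.

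**What to change.** In SAP 11.4.2.2 a, b and c, replace the censoring sentence with: *If no event occurred by the landmark, time = (min(date of last information on that endpoint, date of first ATO infusion + nominal 6 or 12 months) − date of first ATO infusion)/30.5, censored, per 12.4.3.2.* At 30.5 days per month the nominal landmarks are 6 × 30.5 = 183 and 12 × 30.5 = 366 days. A nominal landmark avoids depending on a visit date that may not exist, for example when a patient misses M6 but attends M9.

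Write the event time as *(event date − date of first ATO infusion)/30.5*.

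Two clarifications belong with this edit. The parenthesis in 12.4.3.2 names only progression and death, so state that the rule also covers failure-free survival. Protocol 10.4.2 counts dropout without follow-up information after a toxic study-drug outcome, during primary treatment, as efficacy failure, so say whether that carries over to failure-free survival.

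The cost is a wording change and about one line of programming per endpoint. The last information date is already needed for 12.4.3.2. The estimates may come out slightly lower than under nominal-Vi censoring.
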